From historical data on pregnancies at ChristianaCare Health System, we estimated a historical preterm birth rate of 9.1%. The sample size estimation is based on simulations of co-primary outcomes based on a simulated distribution of gestational age with a singleton preterm birth rate of 9.1%, and an effect of intervention based on literature data²⁶⁻²⁸, with α -level spending of 0.05 shared between co-primaries using Holm's method.

Given shut-down of the study due to the SARS-CoV-2 pandemic, the sample size for the study is estimated to be approximately 1,453 subjects in the prospective arm, and approximately 10,000 in the historical control group. In the primary and alternative analyses, more than 10,000 subjects may meet the eligibility criteria for the historical control group and have the required data, and if so, they will be included in the study.

Power and sample size for this study are affected by factors including the proportion of prospective subjects receiving PreTRM® risk scores at or above the threshold of 16% risk (the study Screen Positive Rate (SPR)), the proportion of higher-risk subjects complying with interventions (compliance), and the rate at which subjects and their neonates remain in the study (retention). For the purpose of power and sample size estimation and based on study monitoring, we estimate that 34% of subjects in the pre-pandemic portion of the prospective arm had PreTRM® risk scores at or above the threshold of 16% risk (the SPR).

Power and sample size are also affected by the study population's baseline level of risk of adverse neonatal outcomes related to prematurity, the sensitivity of testing in identifying at-risk pregnancies, retention of subjects in the study and the efficacy of the interventions as implemented in the study. Literature²⁶⁻²⁸ indicates that the effect of treatment is not constant across different values of GAB. Thus, there is no single value of the effect size in terms of proportion of subjects with NMI less than 3, or mean length of stay. Rather, the effect size is larger for subjects with earlier GAB, while the effect size is reduced for subjects with later GAB.

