For these reasons, power and sample size were estimated based on simulations, using a range of possible values for the factors noted above. These simulations used the observed distribution of GAB from previous studies, adjusted to match the expected overall preterm birth rate of 9.1% in this study. Treatment effect was modeled as a shift in the GAB corresponding to the effect sizes reported in published studies of preterm birth prevention that were based on single treatment modalities, and with extrapolated treatment effects estimating additive effects of bundled interventions.

For the first co-primary endpoint, reduction of severe composite morbidity/mortality, a range of the possible expected effect size can be inferred from the simulations. In the simulations, the proportion of subjects with NMI ≥ 3 is expected to be between 0.023 and 0.02 in the prospective arm and near 0.036 in the control arm based on a previous clinical utility study (Sera Prognostics: data on file). Assuming these proportions, a one-

sided Fisher's Exact test, a sample size of approximately 1,453 subjects with outcomes in the prospective arm with 55% compliance among higher risk subjects and about 10,000 historical controls provides power of 0.7 – 0.9 (NCSS PASS 2020, module "Group-Sequential Tests for Two Proportions").

For the second co-primary test, length of neonatal hospital length of stay from time of birth up to neonatal discharge is assessed by Cox proportional hazards regression with stratification. The hazard ratio based on simulations is expected to be between 1.32 and 1.46 based on a previous clinical utility study (Sera Prognostics: data on file). Assuming these hazard ratios, a sample size of approximately 1,453 subjects with outcomes in the prospective arm with 55% compliance among higher risk subjects and about 10,000 historical controls provides power of 0.8 – 1.0 (NCSS PASS 2020, modules "Group-Sequential Tests for Two Hazard Rates" and "Tests for Two Survival Curves Using Cox's Proportional Hazards Model"). Stratification is indicated based on non-proportionality observed in previous studies.

The two co-primary endpoints provide independent measurements of improved neonatal outcomes. Due to their correlation, there may be modest power to be gained from having two co-primary endpoints. The estimated study power for the combination of the two co-primary endpoints is 0.8 – 1.0.

5 Statistical Analysis

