5.1 Analysis Populations

One control population will be considered in primary analyses: the historical control population. The historical control population includes all subjects who attended ChristianaCare during the eligibility period and who satisfy all eligibility criteria.

The historical control arm will be the control population for primary and alternative analysis of the primary, secondary and exploratory endpoints.

Seven subject populations will be considered in the analyses: an Intent-to-Treat (ITT) population, a modified ITT population, a completer(s) population, a compliant completers population, a non-intervention completers population and a safety population. The completers, compliant completers, non-intervention completers and modified ITT populations are subsets of the ITT population.

The ITT population includes all historical subjects selected and all prospective patients enrolled regardless of whether or not the co-primary outcomes were observed, or in the prospective arm, any PreTRM test result has been generated or intervention consent has been signed. Subjects with missing outcomes will be handled as described in the missing data sensitivity analyses.

The modified ITT (mITT) population includes all subjects for whom both co-primary outcomes are known; and who have either been selected for the historical control group, received a not-higher-risk PreTRM® test result, or consented to and initiated treatment before 24^{0/7} weeks gestation after receiving a higher risk PreTRM® test result.

The completers population includes subjects for whom both of the co-primary outcomes are known, and, in the prospective arm, for whom a PreTRM® test result was generated.

The compliant completers population includes ITT subjects who have missed no more than 20% of daily doses for both low-dose aspirin and vaginal progesterone, and participated in weekly care management calls with no more than 20% missed weeks.

The non-intervention completers population includes all ITT subjects who received a higher-risk PreTRM® test result but neither consented to nor initiated treatment before 24^{0/7} weeks gestation.

The safety population includes all eligible subjects who gave consent to participate in the study and attempted a blood draw for the PreTRM® test, regardless of receipt of study interventions.

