The use of antenatal corticosteroids will be assessed in relation to primary, secondary and exploratory endpoints, and will be compared between the preterm prevention arm and historical controls, and between higher risk and not higher risk subjects in the preterm prevention arm. Optimal timing of dosing of antenatal corticosteroids is herein defined as 2 to 7 days (inclusive) prior to delivery at less than 37 weeks of gestation. Use of antenatal corticosteroids will be expressed as a binary variable: were steroids given in the optimal interval between dose and delivery? Significance of interaction between optimally timed use of antenatal corticosteroids and the specified treatment groups will be assessed in regression as an interaction term: (binary variable) * group. This analysis will be performed without adjustment, adjusted for covariates as specified for the primary analysis, and adjusted via propensity scoring as specified for the alternative analysis. Missing values will be addressed as previously specified for exploratory analyses: by omission of subjects with missing values and by replicating the analysis with multiple imputation of missing values.

Primary, secondary and exploratory endpoints will be assessed in the prospective portion of the mITT population as dependent responses to nonrandom quantitative assignment of treatment⁴². The independent quantitative assignment variable will be the PreTRM® risk score. The functional relationship between endpoints and the risk score will be estimated for the prospective arm. A discontinuity at the intervention threshold in the relationship between outcome and risk score observed in the prospective arm will demonstrate intervention effect, measured as the estimated magnitude of the discontinuity and re-assessed as the estimated risk-score dependent difference between compliant completers and non-intervention completers. As this analysis involves only prospective subjects, it is independent of any selection biases or epoch effects present in comparisons of the prospective arm relative to historical controls. To adjust for any biases present within the

prospective arm, the analysis will be performed without adjustment, adjusted for covariates as specified for the primary analysis, and adjusted via propensity scoring as specified for the alternative analysis.

The primary, secondary and exploratory endpoints will be applied to comparisons within the mITT population.

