- a) The higher-risk group will be compared to the not-higher-risk group within the prospective arm, for tests of equivalence. This comparison is independent of any selection biases or epoch effects present in comparisons of the prospective arm relative to historical controls.
- b) The not-higher-risk group of the prospective arm will be compared to historical controls to assess test sensitivity. It is expected that there will be significant differences in baseline characteristics between the two groups. The analysis will be performed without adjustment, adjusted for covariates specified for the primary analysis, and adjusted via propensity scoring as specified for the alternative analysis.
- c) The higher-risk group in the prospective arm will be compared to a control comparator group estimated as the difference between the control group and the not-higher-risk group, to assess efficacy of the intervention strategy. For count endpoints, direct subtraction of counts (adjusted for arm size) will be used to estimate the comparator group. For non-count endpoints, a number of most similar outcomes proportional to arm size will be removed from the control comparator group for each subject in the not-higher-risk group. It is expected that there will be significant differences in baseline characteristics between the two groups. The analysis will be performed without adjustment, adjusted for covariates specified for the primary analysis, and adjusted via propensity scoring as specified for the alternative analysis.

The following exploratory outcomes will be examined using only the descriptive statistics described above.

- Birthweight
- Number of days of mechanical ventilation

- Amount of surfactant administered
- Occurrence of birthweight <1500g and <2500g
- Individual components of composite morbidity/mortality index
- Whether or not a neonate received surfactant
- Occurrence of pneumonia
- Occurrence of 5-minute Apgar<7
- Occurrence of asphyxia
- Occurrence of preeclampsia
- Occurrence of gestational diabetes mellitus
- Rate of PPROM
- Rate of preterm delivery not associated with PPROM
- Baseline and on-treatment progesterone levels determined by LC-MS

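### Arm size is undefined in exploratory comparison (c); read as the mITT arm, it inflates the derived higher-risk comparator, so an intervention with no effect looks beneficial

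*SAP*

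**What the plan says.** SAP Section 5.7 introduces comparisons (a) to (c) with "The primary, secondary and exploratory endpoints will be applied to comparisons within the mITT population". In comparison (c) the higher-risk women of the prospective arm are set against a "control comparator group estimated as the difference between the control group and the not-higher-risk group, to assess efficacy of the intervention strategy".

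Two rules build that comparator:

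- Count endpoints: "For count endpoints, direct subtraction of counts (adjusted for arm size) will be used to estimate the comparator group".
- Non-count endpoints: for each not-higher-risk woman, the most similar control outcomes are removed, in a number proportional to arm size.

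Neither rule says which arm size is meant.

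Section 5.1 defines mITT. It keeps every not-higher-risk woman with known co-primary outcomes, but a higher-risk woman only if she "consented to and initiated treatment before 24^{0/7} weeks gestation after receiving a higher risk PreTRM® test result". Controls with known outcomes are all kept.

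Section 4 gives the planning figures: "we estimate that 34% of subjects in the pre-pandemic portion of the prospective arm had" scores at or above the threshold, and "55% compliance among higher risk subjects".

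**The concern.** Subtraction recovers the untreated higher-risk rate only if the not-higher-risk share removed from the controls equals the share the controls contain. mITT breaks this. Leaving out higher-risk women who did not start treatment raises the not-higher-risk share of the prospective arm, while the controls, who have no PreTRM® score, keep their full mixture. Scaled to the mITT arm, the subtraction takes out more not-higher-risk women than the controls hold. Higher-risk events are left over for a denominator that is too small.

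The stated purpose of (c) is to assess the efficacy of the strategy. On this reading an intervention that does nothing would show an apparent benefit whenever the test discriminates and acceptance is incomplete. The covariate and propensity adjustments listed for (c) cannot restore the split, because the score is missing in every control. The bootstrap sensitivity analysis in Section 5.7 equalises numbers, not composition.

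**Working it through.** The SAP gives no figure for (c), so there is none to reproduce. The check uses expected counts with no treatment effect.

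**Inputs from the SAP**
- Prospective arm: 1,453 women (Section 4), all taken as tested with known outcomes.
- Screen-positive rate s = 0.34 (Section 4).
- Acceptance c = 0.55: the compliance figure in the power calculation, used as a proxy for consent and initiation.

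**Assumptions not in the SAP**
- Controls have the same 34:66 split.
- Women who start and women who do not start have equal untreated risk, and there is no epoch effect.
- r, the untreated risk ratio of higher-risk to not-higher-risk women, is varied.

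**Composition**
- Higher-risk: 1,453 × 0.34 = 494. Not-higher-risk: 1,453 × 0.66 = 959.
- Higher-risk kept in mITT: 494 × 0.55 = 272. mITT arm: 959 + 272 = 1,231.
- Not-higher-risk share: 959/1,231 = 77.9%, against 66% of tested women.

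**Where the excess comes from.** Controls scaled to 1,231 contain 0.66 × 1,231 = 812 not-higher-risk women, yet 959 are subtracted. The surplus of 147 displaces higher-risk women. Per retained woman the excess is 147/272 = 0.54 times the risk difference between the groups.

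**Formula**, with the not-higher-risk rate set to 1:

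comparator = [(1 − s + s·c)(1 − s + s·r) − (1 − s)]/(s·c) = [0.847(0.66 + 0.34r) − 0.66]/0.187 = 1.54r − 0.54

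spurious relative reduction = 1 − r/(1.54r − 0.54)

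| r | Comparator | Overstated by | Spurious reduction |
|---|---|---|---|
| 1 | 1.00 | 0% | 0% |
| 1.5 | 1.77 | 18% | 15% |
| 2 | 2.54 | 27% | 21% |
| 3 | 4.08 | 36% | 26% |
| limit | – | 54% | 1 − 1/1.54 = 35% |

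**Example** at r = 2 and the SAP's 9.1% preterm birth rate. The not-higher-risk rate is 0.091/1.34 = 6.8%, and the true untreated higher-risk rate is 13.6%. Scaled control events are 1,231 × 0.091 = 112.0, and not-higher-risk events are 65.1. The remaining 46.9 over 272 women is 17.2%, and 13.6/17.2 = 0.79.

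**Sensitivity to acceptance.** In general, comparator = r + (r − 1)(1 − s)(1 − c)/c. For r from 1.5 to 3 the spurious reduction is 9–16% at c = 0.70, 4–7% at 0.85 and 0% at 1.00.

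**Other readings of arm size**
- All tested women: (0.66 + 0.34r − 0.66)/0.34 = r. The bias is zero at every r.
- Share subtracted on the mITT scale but divided by 0.34: (0.66 + 0.34r − 0.779)/0.34, which is 1.15 at r = 1.5 and 2.65 at r = 3. A null intervention then appears to raise risk by 31% and 13% respectively.

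**Non-count rule**, with 10,000 controls. mITT scaling removes 10,000/1,231 = 8.13 controls per not-higher-risk woman, about 7,790, leaving about 2,210. Scaling to 1,453 removes 6.88 each, about 6,600, leaving 3,400. The extra 1,190 or so removed are those most like not-higher-risk outcomes, so the comparator is skewed the same way.

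**The case against.** The strongest reply is that the SAP never says to scale to the mITT arm. The only prospective arm size it states is 1,453, which includes higher-risk women who did not comply, and scaling to that number gives no bias. A reader might infer that the plan, as written, builds in a 15–26% advantage for the intervention. The documents do not support that:

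- The scaling term is undefined, and one mixed reading reverses the direction.
- The range depends on an untreated risk ratio of 1.5 to 3, which the SAP does not give.
- The 55% is a power-planning figure for compliance. mITT needs only consent and initiation, so retention may be higher and the bias smaller.
- The 34:66 split in controls is inferred. They were never scored, and Section 3.4 keeps women who failed assay-related criteria.
- Self-selection among women who accept is a separate problem of unknown direction and cannot be assumed to add to this one.

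It is also fair to say that (c) is one of many exploratory analyses. Section 6.1 concedes that incomplete acceptance brings a bias that cannot be directly adjusted. Section 5.7 also plans ITT and completers replications and a within-arm discontinuity analysis.

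All of this limits the size and the consequence. It does not remove the defect. Section 5.7 places (c) within mITT, so the mITT arm is the natural reading. The other analyses do not correct (c), and this component, unlike self-selection, can be removed by arithmetic.

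**Conclusion.** The point holds in conditional form. Comparison (c) leaves its scaling undefined. On the natural reading, the derived comparator is overstated whenever the test discriminates and some higher-risk women do not start treatment. At 34% screen-positive and 55% acceptance, the spurious relative reduction runs from 0% when the test does not discriminate to a ceiling of 35%, and is 15–26% for risk ratios of 1.5 to 3. It shrinks as acceptance rises and vanishes at full acceptance. These sizes rest on the assumed risk ratio, the compliance proxy, an equal split in controls, and equal untreated risk in women who do and do not start. The co-primary and secondary tests are untouched by this step. What is at stake is the credibility of one exploratory efficacy estimate.

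**What to change.** Define the scaling in (c), for both rules, as all prospective women with a test result and known outcomes, including higher-risk women who did not start treatment. Section 5.1 already has this group as the prospective part of the completers population. For counts:

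comparator rate = (control rate − (1 − SPR) × not-higher-risk rate)/SPR

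where SPR is the observed screen-positive rate in that group. For non-count endpoints, the number of control outcomes removed per not-higher-risk woman should be the number of controls divided by the size of the same group.

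Bootstrap both arms for the interval, since the comparator is itself estimated. Report the comparison for all higher-risk women alongside the one for those who started treatment, and note that the latter remains open to self-selection. This second comparison is a choice of estimand, not part of the scaling correction. State that equal SPR in controls is an assumption.

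The cost is a few lines of SAP text, minor programming, and an estimate less favourable than mITT scaling would give.

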5.4 Primary and Alternative Analyses

The primary and alternative analyses will be performed in the modified ITT (mITT) population on the primary, secondary and exploratory endpoints.

The primary analysis is regression with covariates as specified for each endpoint.

The alternative analysis is regression with covariates as specified for each primary, secondary and exploratory endpoint, with weighting by inverse propensity score to address potential selection bias.

Propensity-matched and unadjusted “raw” analyses are pre-specified as exploratory analyses. These analyses will be performed on primary and secondary endpoints.

In analysis combining primary, alternative and exploratory analyses, we will present the demographic and baseline characteristics differing between the prospective arm and historical controls, selected from among the covariates prespecified for the primary and alternative analyses. We will compare the primary analysis using prespecified covariates, the alternative analysis using IPW, and exploratory PSM un-adjusted (raw) data analyses (Table 2). The results from these four distinct methods are expected to show similarity in direction and potentially in magnitude of effect. If differences in direction are observed, further analysis such as double robust propensity score analysis will be conducted.

Variable	Covariate Regression			Inverse Probability Weighted			Matched data			Unadjusted “Raw” data		
	Prospective (N=)	Historical (N=)	p-value	Prospective (N=)	Historical (N=)	p-value	Prospective	Historical	p-value			
Age												
Parity												

Table 2: Baseline Characteristics

For pre-specified analysis populations and for subgroups specified under Subgroup Analyses below, analyses will be conducted to examine the clinically important groups and unbalanced variables between the prospective and historical cohorts.

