Sensitivity analyses will be performed to check uncertainties in our analysis, as well as address basic assumption validation and the effect of unmeasured/unbalanced confounding factors on primary outcomes. The analyses will compare inclusion and omission of covariates in the analyses of primary, secondary and exploratory endpoints in the mITT population. As PTB is an outcome whose consequences are dominated by the lower tail of the gestational age distribution, sensitivity analyses will also examine the effect on effect size estimates of omitting outliers from the analyses.

A sensitivity analysis to control for reduction in subject number in the prospective arm of the mITT population will be performed. The primary and alternative analyses will be replicated as sensitivity analysis with bootstrap sampling of historical controls to the same number of subjects as the prospective arm. If exclusion of any completers from the mITT population is significantly associated with variables specified for the alternative analysis, this analysis will be repeated with such variables included as covariates. Subjects with missing data for required variables will be excluded from the covariate analysis.

A Bayesian Meta-Analysis will be performed on the data from this study and relevant previous studies. This will be described in a separate document.

Health Economic Outcomes:

Total cost of hospital care for each of the mother and neonate beginning at initiation of care through primary delivery and a gestational age of 40^{0/7} weeks in prospective vs. historical subjects. Analysis of these outcomes is covered in a separate SAP entitled SEAR.

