6.2 Potential differences between historical and prospective cohorts

The assessment of selection bias involves assumptions regarding inclusion or participation by potential subjects, and results can be highly sensitive to assumptions. Even with external validation data, which may work for unmeasured confounders, it is difficult to account for more than a trivial amount of selection bias. Self-selection bias in consenting of higher-risk subjects to interventions further depends on PreTRM® score, a

factor measured only in the prospective arm. Assessment of epoch bias adds assumptions regarding the composition of standard care and incidence of comorbid conditions due to public health trends. Since the study population is a hybrid of prospective cohort and historical cohort, instead of randomized clinical trial, bias is the key issue in the analysis of outcomes. Using appropriate methods to address bias is critical in the study. Different approaches have been applied, including multivariate analysis with covariate adjustment in the studies in which selection bias needs to be handled, and more recently, propensity scoring. Propensity score analysis, includes subgroups defined by propensity score, propensity score used as a covariate in multivariate analysis, matched patients in two groups by propensity score, and inverse probability weighting. Methods based on propensity scores have become important in addressing selection bias in recent years. Other methods are instrumental variable and regression discontinuity design (RDD).

Comparison of diverse adjustment methods as specified in the primary, secondary and exploratory analyses will enable assessment of the degree of selection and epoch bias in the study, and the quality of prespecified and exploratory adjustments for bias.

As well, exploratory analyses within the prospective arm will provide additional estimates of intervention efficacy without reference to historical controls.

Statistical Analysis Plan for AVERT Economic Study (SEAR, Separate Document)

REFERENCES

- 1 Anderson, Robert N, and Betty L Smith. 2003. “Deaths: Leading Causes for 2001.” *National Vital Statistics Reports : From the Centers for Disease Control and Prevention, National Center for Health Statistics, National Vital Statistics System* 52 (9): 1–85. <http://www.ncbi.nlm.nih.gov/pubmed/14626726>.

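### The SAP's sensitivity analyses claim to address unmeasured confounding, but the methods named inform only on imbalance in measured covariates

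*SAP*

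**What the plan says.** Near the end of section 5.7 the sensitivity analyses are given an aim, and the next sentence gives the method. Together they say that these analyses will "address basic assumption validation and the effect of unmeasured/unbalanced confounding factors on primary outcomes. The analyses will compare inclusion and omission of covariates"; the comparison covers the primary, secondary and exploratory endpoints in the mITT population. Two further checks follow. One is on extreme values: "sensitivity analyses will also examine the effect on effect size estimates of omitting outliers from the analyses". The other repeats the primary and alternative analyses with "bootstrap sampling of historical controls to the same number of subjects as the prospective arm".

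Two other sections bear on how the results would be used. Section 5.4 compares covariate regression, inverse probability weighting, matching and the unadjusted analysis: "The results from these four distinct methods are expected to show similarity in direction and potentially in magnitude of effect". It calls for more work, such as a doubly robust propensity analysis, only if the directions differ. Section 6.2 says: "Comparison of diverse adjustment methods as specified in the primary, secondary and exploratory analyses will enable assessment of the degree of selection and epoch bias".

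The SAP is also candid about limits. Section 6.1 accepts that bias from incomplete acceptance of intervention cannot be adjusted directly, because controls have no PreTRM risk score. Section 6.2 says of selection bias that "it is difficult to account for more than a trivial amount of selection bias".

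**The concern.** The prospective women consented to join a study (section 3.4). Under section 5.1, higher-risk women enter the mITT population only if they also consented to and started treatment before 24 weeks. Controls were selected from records by similar eligibility criteria, with no consent step. Differences such as willingness to join research or engagement with prenatal care are therefore a leading rival explanation for any benefit seen, and they are not among the covariates in section 5.3.

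The SAP recognises this and assigns the question to checks that cannot answer it. If the estimates barely move, a reader could take that as evidence against unmeasured confounding when no such test was made.

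**Working it through.** No figure in the SAP is in dispute, so there is none to reproduce. The check has four steps.

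**1. What each named check can detect.**

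| Check (SAP section) | Uses | Shows an unmeasured factor? |
|---|---|---|
| Covariates in versus out (5.7) | measured covariates | No |
| Outliers omitted (5.7) | outcome values | No |
| Controls resampled to equal arm size (5.7) | arm size | No |
| Regression, weighting and matching compared (5.4, 6.2) | measured covariates | No; all share the assumption in question |
| Doubly robust fallback (5.4) | measured covariates | No |

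The fourth method in section 5.4, the unadjusted analysis, uses no covariates at all.

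**2. Demonstration with no true effect.** Simulation: 1,453 versus 10,000 women, 200 runs, three measured covariates, and an unmeasured binary factor U that is independent of them. The odds ratios and prevalences of U are assumptions. Rejection is one-sided at 5%.

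| U: odds ratio; prevalence prospective vs control | OR raw | OR adjusted | OR with U added | Rejection raw / adjusted / with U |
|---|---|---|---|---|
| 3.0; 20% vs 45% | 0.744 | 0.744 | 1.01 | 55% / 54% / 4% |
| 2.5; 10% vs 30% | 0.797 | 0.798 | 1.00 | 27.5% / 27.5% / 3% |

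Raw and adjusted log odds ratios differed by only 0.007 to 0.008 on average. The in/out comparison looks stable while the whole effect is bias.

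**3. Strength needed at the planning effect.** Section 4 expects NMI ≥3 in 0.020 to 0.023 of the prospective arm and about 0.036 of controls, with about 10,000 controls.

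- RR = 0.020/0.036 = 0.556, and 0.023/0.036 = 0.639.
- E-value = r + √(r(r−1)) with r = 1/RR. This gives 1.80 + √(1.80 × 0.80) = 3.00, and 1.565 + √(1.565 × 0.565) = 2.51.
- Upper 95% limit = exp(ln RR + 1.96 × SE), with SE = √((1−p₁)/(n₁p₁) + (1−p₀)/(n₀p₀)). The same E-value formula is then applied to the limit.

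Two values of n₁ are shown. Section 4 gives 1,453 with outcomes. If that count is before the mITT exclusion, then 34% screen-positive × 45% not accepting (1 − 55% compliance) = 15.3% drop out, and 1,453 × 0.847 ≈ 1,231 remain.

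| n₁ | p₁ | SE | Upper limit | E-value for limit |
|---|---|---|---|---|
| 1,453 | 0.020 | 0.191 | 0.807 | 1.78 |
| 1,453 | 0.023 | 0.179 | 0.907 | 1.44 |
| 1,231 | 0.020 | 0.206 | 0.832 | 1.69 |
| 1,231 | 0.023 | 0.193 | 0.932 | 1.35 |

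The two-sided 95% limit corresponds to a one-sided 0.025 test, the first Holm step for two hypotheses.

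**4. What those E-values do not mean.** For a binary factor with outcome risk ratio s, the bias factor is (1 + p₀(s−1))/(1 + p₁(s−1)), where p₀ and p₁ are now its prevalences in controls and the prospective arm. Take s = 1.35 and assumed prevalences of 40% and 30%: 1.140/1.105 = 1.03, against the 1/0.932 = 1.07 needed. Take s = 1.69 with 40% and 24%: 1.276/1.166 = 1.09, against 1/0.832 = 1.20. Neither removes significance. The E-value is a worst-case minimum.

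**The case against.** Several points on the other side stand.

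- The aim covers unbalanced as well as unmeasured factors, and the covariate comparison does serve the unbalanced part. Only the unmeasured part fails.
- Section 5.7 plans exploratory analyses inside the prospective arm: a discontinuity analysis at the risk-score threshold, and a comparison of higher-risk with not-higher-risk women. These avoid historical controls and so avoid arm-versus-control confounding. The mitigation is partial. They do not quantify bias in the co-primary comparison, and the threshold analysis uses the mITT population, from which higher-risk decliners have already been removed on one side of the cut-off.
- Sections 6.1 and 6.2 warn openly about bias. A reader might infer that the final report will claim that unmeasured confounding was ruled out. The SAP contains no such rule. What it does contain is the expectation of agreement in section 5.4 and the claim for comparing methods in section 6.2, which make that over-reading easy.
- A reader might infer from step 3 that any confounder of strength 1.35 to 1.8 would overturn the result. Step 4 shows otherwise.
- Deleting the word for unmeasured factors would by itself cure the misstatement. That is true, but it would leave the SAP with no analysis of how strong an unmeasured factor would need to be to overturn the co-primary result.

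**Conclusion.** The concern holds in a limited form. The sensitivity analyses in section 5.7, and the comparison of adjustment methods in section 6.2, inform on measured imbalance only, so the SAP claims more for them than they can deliver.

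The size is indicative. At the planning effects, an unmeasured factor would need a risk ratio of at least 2.5 to 3.0 with both arm and outcome to explain the estimate fully. To bring the upper limit to 1 it would need at least about 1.4 to 1.8 (1,453 analysed) or 1.35 to 1.7 (about 1,231). These are minimum strengths that could suffice in the worst case. They rest on the planning proportions for NMI ≥3, whereas the specified test is a weighted ordinal regression, and nothing has been computed here for NNOLOS. The simulation shows the mechanism under assumed values; it does not estimate the bias in this trial.

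**What to change.** In section 5.7, state that the comparison with and without covariates assesses measured imbalance. Limit the section 6.2 claim for comparing adjustment methods in the same way.

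For unmeasured confounding, prespecify for both co-primary endpoints:

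- an E-value for the estimate and for the confidence limit, on a stated effect scale;
- a tipping-point table, crossing the difference in confounder prevalence between arms with its association with the outcome, showing where the Holm-adjusted result is lost;
- a benchmark against the strongest measured covariate.

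This takes a few lines of text and a table computed from the fitted models, with no new data and no change to the primary tests. The cost is a little extra analysis and possibly a less favourable statement of robustness.
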